3. STUDY DESIGN

Patient Cohort

This is a prospective cohort study using samples from all patients enrolled in the TAR:GET-1 (170 patients, 85 in each arm). The TAR:GET-1 trial will recruit patients starting in June 2019, over a period of 4 years, and patient will be followed up with further biological samples taken over a further period of 4 years. This will need to be analysed for which we estimate a further 2 years. The total duration of the study is therefore 10 years starting June 2019.

We aim to collect all samples from each patient to maximise the information obtained, whilst incurring negligible extra risk to the study participants.

Some of the samples are already obtained as part of the TAR:GET-1 protocol and we will use left over material to carry out analyses.

Some of the samples are not routinely obtained for TAR:GET-1 enrolment, but the TAR:GET-1 protocol and consent process covers their (optional) collection.

The only extra samples that requires a new consent process as part of M.O.T.-AMR is an optional post-treatment protocol biopsy.

The study aim is to be a comprehensive assessment of antibody-mediated rejection biomarkers pre- and post-treatment, but has below been artificially divided into Parts 1 and 2, Part 1 being funded by Imperial BRC, Cambridge BRC and NIHR EME (funding secured) whereas applications for funding for Part 2 are in process. A funding approval letter will be provided to the Sponsor and REC committee prior to commencing any element of part 2 of the study, and will specify which further specific elements of the study have received funding approval.

Samples taken as part of TAR:GET-1:

Patients enrolled in TAR:GET-1 will have a number of samples taken, and consent for enrolment in TAR:GET-1 includes agreement to the use of extra material left after diagnosis for research. We will therefore be able to access in 100% of patients enrolled in TAR:GET-1:

- Enrolment biopsy material
- Serum samples taken for DSA measurements
- Post-treatment indication biopsies taken as part of routine clinical care.

TAR:GET-1 is already assessing DSA MFI, DSA target and B lymphocyte numbers at baseline and 3 months post-treatment. In addition to these, M.O.T.-AMR will analyse in left over material from these routine samples:

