Specifically for M.O.T-AMR, patients enrolled in TAR:GET-1 will be offered an optional protocol biopsy at 6 months post-treatment. This additional sample is optional and M.O.T.-AMR is not dependent on it being obtained. This protocol biopsy will be carried out in the local centre, by the local clinical team. A post-treatment protocol biopsy is a biopsy taken in a patient with stable transplant function and no indication for a biopsy to be taken. The literature suggests that this a useful tool for monitoring response to treatment (Viglietti 2018a), but strong evidence from randomised controlled trials such as TAR:GET-1 is lacking for its routine introduction into clinical care and therefore, in most centres a post-treatment protocol biopsy is not offered to patients. The protocol biopsy will be collected for research and costed as research. Biopsy results on these protocol biopsies will be made available to the clinicians if any unexpected findings that need to be acted upon for patient benefit are noted. We will carry out the same histological and transcriptional investigations on these biopsies as for the enrolment and indication biopsies. A conservative estimate of protocol biopsy acceptance is 50%, based on our local experience (85 samples), and this is the number of samples we aim to achieve.

Funding:

Part 2: Funding for taking these biopsies is covered by NIHR EME 129029. Shipping and analysis will be partly covered by Imperial BRC.

This table illustrates how visits and samples in TAR:GET-1 will be used for investigations in M.O.T.-AMR. The additional samples needed for M.O.T.-AMR are in italic.

TAR:GET-1 trial visits	Baseline	Unscheduled	Visit 3 (month 3)	Visit 4 (month 6)	Visit 5 (month 12)
Biopsy histology and gene expression analysis	Use leftover sample	Indication biopsy for graft dysfunction: Use leftover samples		Optional protocol biopsy	
Serum DSA characteristics and BAFF	Use leftover sample		Use leftover sample		Use leftover sample
B cell characteristics and Peripheral blood transcriptomics	2 extra blood tubes		2 extra blood tubes	2 extra blood tubes	2 extra blood tubes

Sample storage:

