7. STATISTICS AND DATA ANALYSIS

The patient cohort size is dictated by TAR:GET-1: 170 patients, 85 in each arm. Under plausible modelling assumptions, for any biomarker that is on the mechanistic pathway between treatment and primary outcome, the power of the main study (90%) will be matched or exceeded when comparing the mean biomarker values between treatment groups. The mediation analysis will estimate for each biomarker the influence on allograft survival rate per unit change in biomarker, above and beyond, the direct effect of treatment. This will decompose the overall, marginal, treatment effect into a proportion attributable to a mechanism via the biomarker, and the complement attributable to direct effects, or other mechanisms. A similar multivariable analysis will proceed to estimate the mediation effects of multiple biomarkers acting in parallel, as an exploratory analysis using variable selection methods to control for over-fitting.

Data from this research project will be merged and linked with data from the TAR:GET-1 clinical trial by the statistician team.

Descriptive data

Mechanistic Evaluation of Treatments for Acute Antibody-Mediated Rejection of the Kidney Transplant (M.O.T. AMR) – Version 1.4 27/05/2020

This will include description of all the biological characteristics analysed in 2 populations (rituximab + SOC and SOC) at baseline and at all follow-up time points. Summary statistics (mean, median, SD, range for continuous variables, and frequency tables for categorical variables) will be reported broken down by treatment, with exploratory figures (box-and-whisker plots for continuous, and stacked bar-charts for categorical).

Outcome analysis

Appropriate measures of differences between treatment groups will be estimated with point estimates, 95% confidence intervals, and p-values. Depending on the type of variable (continuous, categorical, time-to-event), regression techniques (linear, logistic, cox) and transformation of the endpoints will be considered.

Differences in characteristics comparing pre- to post-treatment samples at sequential time points will be analysed comparing the 2 groups of patients (SOCR versus SOC) using mixed effect models repeat measurement techniques.

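### The aim of 85 six-month protocol biopsies makes no allowance for patients who cannot have one, and even 85 does not carry the protocol's general 90% power statement over to six-month tissue markers

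*Protocol*

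**What the plan says.** Section 3, under the optional post-treatment biopsy, makes a general offer: "patients enrolled in TAR:GET-1 will be offered an optional protocol biopsy at 6 months post-treatment". It then defines the procedure: "A post-treatment protocol biopsy is a biopsy taken in a patient with stable transplant function and no indication for a biopsy to be taken". The planning figure follows in the same paragraph: "A conservative estimate of protocol biopsy acceptance is 50%, based on our local experience (85 samples", and of that count the protocol says "this is the number of samples we aim to achieve". The paragraph also states: "This additional sample is optional and M.O.T.-AMR is not dependent on it being obtained".

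The other source of post-treatment tissue, listed earlier in section 3, is "Post-treatment indication biopsies taken as part of routine clinical care". The visit table shows these as unscheduled and prompted by graft dysfunction. The month-6 protocol biopsy is the only post-treatment tissue sample tied to a visit.

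Section 7 opens with "The patient cohort size is dictated by TAR:GET-1: 170 patients, 85 in each arm". It goes on to say that, under plausible modelling assumptions, comparing mean values between arms will have at least the main trial's 90% power for any biomarker on the pathway from treatment to outcome. It makes no exception for markers measured in only part of the cohort. Section 2 includes end-organ damage, assessed by histology and transcripts, in the primary objective.

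**The concern.** Two statements in the protocol do not fit together.

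- **Denominator.** The count of 85 applies 50% to every enrolled patient, but the definition beside it admits only patients who are stable and have no indication at month 6. Section 4.4 also removes anyone who withdraws from TAR:GET-1. All patients enter with biopsy-proven acute rejection (section 1.2), and the visit table itself foresees indication biopsies for dysfunction. Some will therefore probably fall outside the definition, and the count shows no allowance for them.
- **Power.** Section 7 rests its statement on 170 patients and applies it to any pathway biomarker. Six-month histology and transcript markers are planned in about half that number.

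At stake is how a null result for the tissue markers is read. Someone relying on section 7 would take a non-significant six-month difference as coming from a comparison with at least 90% power, when the planned number may give much less.

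**Working it through.** **Inputs from the protocol.** Cohort 170, 85 per arm (section 7). Acceptance 50% and aim 85 (section 3). Claimed power 90% or more (section 7).

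**Assumptions, because the protocol gives no figure.** Share *s* of patients eligible at month 6. Two-sided alpha 0.05. Biopsies split equally between arms. Normal approximation for a difference in means.

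**Step 1: reproduce the stated figure.** 170 × 0.50 = 85. This is exact, so the 50% was applied to the whole cohort.

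**Step 2: apply 50% to eligible patients only.** Expected number = 170 × *s* × 0.50. Acceptance needed to reach 85 = 85 / (170 × *s*). The last column is the binomial probability of at least 85 at 50% acceptance, with the eligible number rounded to a whole patient.

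| Ineligible | Eligible | Expected biopsies | Acceptance needed for 85 | P(at least 85) |
|---|---|---|---|---|
| 0% | 170 | 85 | 50% | 0.53 |
| 5% | 161.5 | 80.8 | 52.6% | 0.29 |
| 10% | 153 | 76.5 | 55.6% | 0.10 |
| 20% | 136 | 68 | 62.5% | 0.002 |
| 30% | 119 | 59.5 | 71.4% | <0.001 |

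With 3% or fewer ineligible, the expected number is 82.5 or more and the shortfall is trivial.

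**Step 3: carry the numbers to section 7.** Take a marker whose difference has exactly 90% power at 170. The sum of the normal quantiles is 1.960 + 1.282 = 3.242. The standardised difference is 3.242 × √(2/85) = 0.497. With *n* biopsies in total, power = Φ(3.242 × √(*n*/170) − 1.960).

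- *n* = 85: Φ(2.292 − 1.960) = Φ(0.332) = 63%
- *n* = 76: Φ(2.167 − 1.960) = Φ(0.207) = 58%
- *n* = 68: Φ(2.050 − 1.960) = Φ(0.090) = 54%

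The halving alone takes 90% to 63%, a loss of 27 points. Ineligibility of 10 or 20% takes a further 5 or 9 points.

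**Step 4: what 90% power at 85 would require.** The standardised difference would have to be 3.242 × √(2/42.5) = 0.703 instead of 0.497. At 170 patients such a marker would have power Φ(3.242 × √2 − 1.960) = Φ(2.624), about 99.6%.

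**The case against.** The arithmetic 170 × 50% = 85 is correct. A reader might infer that the stated number will not be delivered, or that 85 is close to a ceiling. The documents support neither reading:

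- The eligible share is not given, and the denominator of the local 50% is not stated. If that rate was biopsies obtained per patient treated, ineligibility is already inside it.
- The protocol calls 50% conservative. Acceptance of 53 to 63% would still reach 85 with 5 to 20% ineligible. If everyone eligible accepted, 20% ineligible would leave 136 biopsies.
- The 85 is an aim for an optional sample on which the study says it does not depend. It is not a powered sample size.

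All of this stands, and it limits the first half of the point to an allowance that is not shown.

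On power, there are three replies:

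- **Section 7 says matched or exceeded, so some markers may have a margin.** True, but step 4 shows how large it must be: about 99.6% power at 170 to keep 90% at 85. The protocol does not claim that.
- **Repeated-measures models may gain precision from the baseline biopsy.** They may, but that gain would be available with 170 follow-up biopsies too, and does not by itself replace missing six-month observations.
- **Indication biopsies also supply tissue and receive the same analyses.** They do, so the protocol biopsy is not the only post-treatment tissue. They are unscheduled and prompted by dysfunction, however, and are not like-for-like six-month measurements.

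A reader might also infer that early patients will miss the biopsy because it is labelled Part 2, and section 3 requires a funding letter "prior to commencing any element of part 2 of the study". The same section says NIHR EME covers taking these biopsies and names NIHR EME among the secured funders. Nothing says the letter is outstanding or that any patient passed month 6 unsampled. This is an inconsistency of labelling only.

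**Conclusion.** The point holds in two limited parts. First, the aim of 85 is 50% of all enrolled patients and shows no allowance for those whom the protocol's own definition excludes. If the 50% means acceptance among eligible patients, the expected number is about 81, 76, 68 or 60 for an assumed 5, 10, 20 or 30% ineligible. A shortfall is possible but not demonstrated.

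Second, and more important, the 90% statement in section 7 does not carry over to six-month histology and transcript markers even if all 85 biopsies are obtained. Power is about 63% at 85, 58% at 76 and 54% at 68, for a marker with exactly 90% at 170. This rests on the assumed alpha, equal split and normal approximation; markers with larger effects would do better. Most of the loss comes from sampling half the cohort, and the eligibility question is the smaller part.

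**What to change.** 1. In section 3, state whether the local 50% is among all treated patients or only those eligible at month 6. Give the expected number as 170 × assumed eligible share × acceptance among eligible patients, with a range. If the 50% already counts all treated patients, say so; 85 then stands as the expected number.
2. In section 7, limit the 90% statement to markers measured in essentially all 170 patients. For six-month tissue markers, state the power or precision at the expected number of biopsies.
3. Separately, reconcile the Part 2 label on the biopsy with the secured NIHR EME funding described in section 3, and say whether the funding-letter condition applies to it.

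The cost is protocol wording and a less favourable stated figure for the tissue markers. No added biopsies, visits or patients are asked for.

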3.1 STUDY OUTCOME MEASURES

Mechanistic Evaluation of Treatments for Acute Antibody-Mediated Rejection of the Kidney Transplant (M.O.T. AMR) – Version 1.4 27/05/2020

Primary outcome is graft survival 4 years post-treatment.

4. PARTICIPANT ENTRY

4.1 PRE-REGISTRATION EVALUATIONS

None

4.2 INCLUSION CRITERIA

All patients enrolled in TAR:GET-1 are eligible.

4.3 EXCLUSION CRITERIA

None. If some patients decline extra samples to be taken for research, we can still analyse left over tissue from routine clinical samples for some aspects of the study.

4.4 WITHDRAWAL CRITERIA

- Subject decision. A subject is free to withdraw consent and discontinue participation in the study at any time
- Patients who withdraw from TAR:GET-1 will also be withdrawn from MOT-AMR and withdrawal criteria is the same as TAR:GET-1.

5. ADVERSE EVENTS

5.1 DEFINITIONS

Adverse Event (AE): any untoward medical occurrence in a patient or clinical study subject.

Serious Adverse Event (SAE): any untoward and unexpected medical occurrence or effect that:

- **Results in death**
- **Is life-threatening** – *refers to an event in which the subject was at risk of death at the time of the event; it does not refer to an event which hypothetically might have caused death if it were more severe*
- **Requires hospitalisation, or prolongation of existing inpatients' hospitalisation**
- **Results in persistent or significant disability or incapacity**
- **Is a congenital anomaly or birth defect**

Medical judgement should be exercised in deciding whether an AE is serious in other situations. Important AEs that are not immediately life-threatening or do not result in death or hospitalisation but may jeopardise the subject or may require intervention to prevent one of the other outcomes listed in the definition above, should also be considered serious.

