5.3 REPORTING PROCEDURES

All adverse events should be reported. Depending on the nature of the event the reporting procedures below should be followed. Any questions concerning adverse event reporting should be directed to the Chief Investigator in the first instance.

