5.3.1 Non serious AEs

All such events, whether expected or not, should be recorded.

Mechanistic Evaluation of Treatments for Acute Antibody-Mediated Rejection of the Kidney Transplant (M.O.T. AMR) – Version 1.4 27/05/2020

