5.3.2 Serious AEs

An SAE form should be completed and faxed to the Chief Investigator within 24 hours. However, relapse and death due to transplantation, and hospitalisations for elective treatment of a pre-existing condition do not need reporting as SAEs.

All SAEs should be reported to the South West -Frenchay Research Ethics Committee where in the opinion of the Chief Investigator, the event was:

- 'related', ie resulted from the administration of any of the research procedures; and
- 'unexpected', ie an event that is not listed in the protocol as an expected occurrence

Reports of related and unexpected SAEs should be submitted within 15 days of the Chief Investigator becoming aware of the event, using the NRES SAE form for non-IMP studies. The Chief Investigator must also notify the Sponsor of all SAEs.

Local investigators should report any SAEs as required by their Local Research Ethics Committee, Sponsor and/or Research & Development Office.

Contact details for reporting SAEs

[contact]

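### Section 5.1 makes unexpectedness part of the SAE definition, which conflicts with section 5.3.2 and leaves the reporting route for foreseeable serious events unclear

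*Protocol*

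**What the plan says.** Section 5.1 (Definitions) gives two definitions. An adverse event is "any untoward medical occurrence in a patient or clinical study subject", with no condition on expectedness. A serious adverse event is "any untoward and unexpected medical occurrence or effect that" leads to one of the listed outcomes, which include death, threat to life and hospital admission. A further paragraph says "Medical judgement should be exercised in deciding whether an AE is serious in other situations"; it addresses important events that fall short of death, immediate threat to life or hospital admission, and it does not mention expectedness.

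Section 5.3 opens with a general duty, "All adverse events should be reported", and then directs the reader to procedures that depend on the type of event. For non-serious events, section 5.3.1 says "All such events, whether expected or not, should be recorded". For serious events, section 5.3.2 says "An SAE form should be completed and faxed to the Chief Investigator within 24 hours" and "The Chief Investigator must also notify the Sponsor of all SAEs". It exempts by name relapse and death due to transplantation, and elective admissions for a pre-existing condition.

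For the ethics committee, section 5.3.2 narrows the SAEs to those that are both related to a research procedure and unexpected. There it explains the second term as "unexpected', ie an event that is not listed in the protocol as an expected occurrence".

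Section 3 (Study Design) describes the study-specific procedure that matters here: an optional protocol biopsy at 6 months, taken when graft function is stable and there is no clinical indication, with 85 samples as the aim.

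**The concern.** Seriousness and expectedness answer different questions. Seriousness decides whether an event needs rapid reporting to the Chief Investigator and the Sponsor. Expectedness decides whether it also needs onward reporting to the ethics committee. Section 5.1 merges the two, so the second question is asked before the first has been settled.

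The biopsy is the only sample that needs a new consent process for this study, and it is taken for research in patients with no clinical reason for it. Its serious complications are therefore the events this section most needs to route clearly. Many of them are foreseeable in the everyday sense of the word, and those are the events for which section 5.1 is ambiguous. At stake are the 24-hour form and the notification of the Sponsor.

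**Working it through.** No figure in the protocol bears on this, so the check is to read the sections against each other and trace one event through them. Take a foreseeable complication of the 6-month research biopsy that leads to hospital admission.

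**Two possible meanings of unexpected in section 5.1**

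- Reading A: the ordinary meaning, that is, not foreseeable. Section 5.1 gives no other.
- Reading B: the meaning in section 5.3.2, that is, not listed in the protocol as expected. The protocol text at hand lists no biopsy complication as expected.

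| Step | Section | Reading A | Reading B |
|---|---|---|---|
| Is it an AE? | 5.1 | Yes | Yes |
| Is it an SAE? | 5.1 | No, it was foreseeable | Yes |
| Is it a non-serious AE? | 5.3.1 | No, it led to admission | No |
| 24-hour form required? | 5.3.2 | Not by the text | Yes |
| Sponsor notified? | 5.3.2 | Not by the text | Yes |
| Ethics committee, if related? | 5.3.2 | No | Yes |
| General duty to report AEs? | 5.3 | Yes, with no deadline or route to the Sponsor | Yes |

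Three things follow.

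1. **The two sections conflict on either reading of the word.** If every SAE is unexpected by definition, SAEs that are related and unexpected are the same set as SAEs that are related. The expectedness filter in 5.3.2 then removes nothing. It has work to do only if some SAEs are expected, which 5.1 rules out.

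2. **Under Reading A the order of protection is reversed.** Expected non-serious events are captured explicitly in 5.3.1, while expected serious events have no matching provision. The medical-judgement paragraph in 5.1 does not close the gap, because it is directed at events outside the listed outcomes. An important event without admission therefore faces no expectedness test, while one with admission does.

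3. **Under Reading B the word does no harm now but is fragile.** Nothing about the biopsy is listed, so nothing is excluded. If a list of expected biopsy events were added later while 5.1 stayed as it is, the listed events would leave the 24-hour and Sponsor routes as well as the ethics-committee route.

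**The case against.** The strongest reply is that the only meaning the protocol gives to unexpected is the one in 5.3.2, and the same word should carry the same meaning in 5.1. On that basis every serious biopsy complication is an SAE and is reported. The surrounding text supports this. All adverse events are to be reported, the named exemptions do not include biopsy complications, and such exemptions would be largely needless if 5.1 already dropped foreseeable events. The separate ethics-committee filter also implies that the authors meant SAEs to include expected events.

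Much of this stands. A reader might infer from 5.1 that known biopsy complications fall out of SAE reporting altogether; the documents do not support that as a necessary result, because it requires Reading A, and the general duty in 5.3 applies even then.

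The reply does not rescue the wording of 5.1. The helpful meaning sits inside a bullet about the ethics committee and is not tied back to the definition, so a site working from 5.1 meets an everyday word with no gloss. The general duty in 5.3 refers onward to two procedures, neither of which fits the event under Reading A. The argument that the authors intended expected events to be SAEs is also an argument for correcting 5.1, since its literal text says otherwise.

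**Conclusion.** The point holds as an internal contradiction in a safety rule. Section 5.1 carries an expectedness condition that belongs only in 5.3.2, and on one reasonable reading a foreseeable serious complication of the research biopsy can miss the 24-hour form and the notification of the Sponsor. On the other reading nothing is excluded. The defect is that the text allows both.

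The size cannot be expressed as a number. A reader might be tempted to apply an assumed complication rate to the 85 planned biopsies. The protocol gives no such rate, and the result would be the chance that a complication occurs, not the chance that one goes unreported. Nor do the documents show that the biopsy would come to look safer than it is: biopsy safety is not among the objectives or outcomes, and assessment and follow-up are placed within TAR:GET-1, whose own safety reporting is not at hand.

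The conclusion rests on two assumptions. One is that a site might read unexpected in its ordinary sense. The other is that no biopsy complication is listed as expected in the protocol; consent material was not available and is not counted either way.

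**What to change.** Delete the words *and unexpected* from the SAE definition in section 5.1, so that seriousness alone decides what is an SAE. Leave expectedness where it already works, as the ethics-committee criterion in section 5.3.2. The event traced above then has a single route on either reading: SAE form within 24 hours, notification of the Sponsor, and assessment for ethics-committee reporting.

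This should not be paired with a new list of expected biopsy events. With nothing listed, any related serious biopsy complication counts as unexpected under 5.3.2 and goes to the ethics committee within 15 days; listing such events would take them out of that route.

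The cost is a two-word amendment and possibly a few more SAE forms. Treatment, endpoints and sample size are unaffected.
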